4.10.1. Adverse Events

Adverse events will be classified by System Organ Class (SOC) and Preferred Term (PT) using the Medical Dictionary for Regulatory Activities (MedDRA Version 17.0). In order to remain consistent in the adverse event data collected in previous trials, the severity of adverse events will be graded by the investigator according to the CTCAE, Version 3.0 whenever possible. The adverse event CTCAE/severity grades include Grade 1 (Mild), Grade 2 (Moderate), Grade 3 (Severe), Grade 4 (Life-threatening), and Grade 5 (Fatal). The relationship of study drug to adverse event has 4 categories: probable, possible, unlikely and unrelated.

A treatment-emergent adverse event (TEAE) is defined as an adverse event that occurs or worsens in the period extending from the day of a subject's first dose of study drug to 4 weeks after the last dose of study drug in this study. In the following analyses, a subject having the

PTC Therapeutics, Inc. – Confidential Page 12 of 24 Version 1.0 14JUL2017 same event more than once will be counted only once. Adverse events will be summarized by worst CTCAE/severity grade.

Total numbers of AEs, TEAEs and serious AEs (SAE) and the number and percentage of subjects experiencing ≥1 TEAE, ≥1 SAE, discontinuation due to AE, and death will be tabulated. The number and percentage of subjects with TEAEs and SAEs will be by Relationship to study drug and CTCAE/severity, respectively.

The number and percentage of subjects experiencing a specific TEAE will be tabulated

- 1) by SOC, and PT
- 2) by SOC, PT, and CTCAE/severity grade
- 3) by SOC in the descending order of the SOC frequency in ataluren group,
- 4) by PT in the descending order of the PT frequency in ataluren group.

The following TEAEs will be analyzed similarly:

- 1) by SOC, and PT and
- 2) by SOC, PT, and CTCAE/severity grade.
 - Possibly or probably treatment-related TEAEs
 - Serious TEAEs and possibly or probably treatment-related serious TEAEs
 - TEAEs leading to discontinuation from treatment
 - Adrenal, hepatic and renal TEAEs and possibly or probably treatment-related adrenal, hepatic and renal TEAEs leading to special diagnosis evaluation
 - TEAEs with CTCAE/severity grade ≥3 and possibly or probably treatment-related TEAEs with CTCAE/severity grade ≥3
 - Common TEAEs (subject frequency of $\geq 5\%$)

Listings of death, serious AEs, AEs leading to discontinuation from treatment, and adrenal, hepatic and renal AEs leading to special diagnostic evaluations will be provided. Renal AEs for subjects not using nephrotoxic concomitant medications, subjects using nephrotoxic concomitant medications, and subjects with postbaseline creatinine > 1.5*ULN will also be listed, separately.

The drug exposure adjusted TEAE incidence rate will be summarized by SOC and PT, where the incidence rate of the TEAE per 100 patient-year = (number of events/number of patient-years) *100. The number of patient-years is defined as the sum of the number of days on study drug of all patients divided by 365.25.

In addition, the number of subjects with clinical laboratory abnormalities, abnormal vital signs, and abnormal electrocardiogram reported as TEAE will be summarized.

Non-serious TEAE will be displayed by SOC and PT. The common non-serious TEAE (subject frequency of ≥5%) will also be displayed by SOC and PT.

Numbers of occurrence of serious TEAE and the numbers of occurrence of non-serious TEAE will be summarized by SOC and PT, separately.

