11.4.5. Primary Variables

11.4.5.1 *Adverse Event*

Adverse events will be classified using the MedDRA classification system. The severity of adverse events will be graded according to the CTCAE, Version 3.0, whenever possible.

A treatment-emergent adverse event is defined as an adverse event that occurs or worsens in severity in the period extending from the day of a subject's first ataluren dose in this study to 4 weeks after the last ataluren dose in this study.

The number and percentage of subjects experiencing a specific adverse event will be tabulated by body system and MedDRA term. A subject having the same event more than once will be counted only once. Adverse events will be summarized by worst CTCAE grade within a subject. Exposure-adjusted incidence rate will be reported.

Adverse events classified as CTCAE Grade 3 or higher; study-drug-related events; hepatic, and renal events leading to special diagnostic evaluations; events leading to discontinuation from treatment; SAEs; and AESIs will be considered with special attention.

11.4.5.2 *Laboratory Data*

Hematological, serum biochemistry, urine data, and their changes (only for continuous laboratory parameters) from baseline will be summarized descriptively for each visit. Hematological, serum biochemistry, and urine data will be graded according to CTCAE severity grade when applicable. For parameters for which a CTCAE scale does not exist, the frequency of subjects with values below, within, and above the normal ranges will be summarized. Summary tables will be presented for each relevant assay to show the number of subjects by severity grade with corresponding percentages. Subjects will be characterized only once for a given assay, based on their worst severity grade observed during the time period of interest.

Separate listings and tables will be created for assessment of hepatic and renal parameters.

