6. ANALYSIS CHANGES FROM PROTOCOL

Due to the premature termination of the study, the time of withdrawal from the study analysis and 48-week completer and whole study completer analyses have been removed compared to current protocol version 1.0. The paried t-test on FEV₁ and the summary analysis of FEF₂₅₋₇₅, CFQ-R domain scores, and ataluren plasma concentrations have also been removed. Additionally the summary of incidences, rates, and durations of interventions (eg, antibiotic use and hospitalization) and disruptions to daily living (eg, missed school or work) resulting from pulmonary symptoms has been removed. On the other hand, the drug exposure adjusted incidence rate of TEAEs has been added. Summary of occurrence of TEAE has been added as well.

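### SAP 4.10.1 does not settle whether the exposure-adjusted TEAE rate counts every event or each subject once, and neither reading gives the incidence rate it is called

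*SAP*

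**What the plan says.** Protocol 11.4.5.1 states the counting rule: "A subject having the same event more than once will be counted only once". Two sentences later it adds "Exposure-adjusted incidence rate will be reported", without a formula.

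SAP 4.10.1 repeats the rule ahead of its list of outputs. For the analyses that follow, a subject having the "same event more than once will be counted only once". Further down the same section it gives the formula: "the incidence rate of the TEAE per 100 patient-year = (number of events/number of patient-years) *100", by system organ class and preferred term. The denominator is "the sum of the number of days on study drug of all patients divided by 365.25". It is not cut off at a subject's first event.

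The section also plans a separate output: "Numbers of occurrence of serious TEAE and the numbers of occurrence of non-serious TEAE will be summarized by SOC and PT, separately". SAP Section 6 lists the exposure-adjusted rate as an addition to the protocol and then, as its own item, says "Summary of occurrence of TEAE has been added as well".

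**The concern.** The rule and the formula stand in one section, and the text does not say which of them fixes the numerator. A programmer who applies the rule as written would count each subject once per term and divide by person-time that keeps running after the event. A programmer who applies the formula as written would count every occurrence. For a frequent term these two tables differ a great deal, and both could claim to follow the SAP.

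This is the only exposure-adjusted adverse event measure in the primary safety analysis. It is needed because follow-up is unequal: SAP 2.1 records early termination on 2 March 2017, when patients had been in the extension for different lengths of time. Protocol 14.2.2 also intends these data to supplement the 48-week double-blind safety data. Under the count-once reading, a measure meant to adjust for exposure would itself change with exposure length.

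**Working it through.** The documents state no adverse event rate for this study, so there is no figure to reproduce. The check has two parts.

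**1. The text**

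- *For count-once:* the rule is addressed to the analyses that follow it, and the rate follows it. The output is called an incidence rate. Occurrences have their own table in 4.10.1 and their own item in Section 6. The protocol also places the rule just before the rate.
- *For all occurrences:* the formula's numerator is worded as events, whereas the incidence tables are worded as subjects and percentages. Total numbers of AEs, TEAEs and SAEs also come after the count-once sentence, so that sentence cannot cover everything below it. Total patient-years is the right denominator for an event rate.

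The text does not decide between them.

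**2. The size of the difference**

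Inputs from the documents:

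- Protocol Section 1: first dosing in the parent study on 15 August 2014, 48 weeks of treatment, estimated recruitment of 14 months.
- SAP 2.1: termination on 2 March 2017.

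Nominal exposure at termination:

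- Earliest entrant: 15 August 2014 + 48 weeks = 17 July 2015; 594 days to termination = 1.63 years (85 weeks).
- Latest entrant: 14 months later, 15 September 2016; 168 days = 0.46 years (24 weeks).
- Mean, if entry is uniform: (594 + 168)/2 = 381 days = 1.04 years.

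Assumptions, not in the documents: uniform entry, no dropout, no gap between the studies, and a constant event rate L per patient-year.

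With T the exposure in years, the three possible measures estimate:

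- (a) all events / total patient-years: L
- (b) subjects counted once / total patient-years: mean(1 − exp(−L·T)) / mean(T)
- (c) subjects with a first event / time to first event or end of follow-up: L

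For T uniform from 0.460 to 1.626 years, mean exp(−L·T) = [exp(−0.460·L) − exp(−1.626·L)] / (1.166·L). At L = 1 this is (0.631 − 0.197)/1.166 = 0.373, so (b) = (1 − 0.373)/1.043 = 0.601, or 60.1 per 100 patient-years.

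| Assumed true rate L | (a) and (c), per 100 PY | (b), per 100 PY | Shortfall of (b) |
|---|---|---|---|
| 0.1 | 10 | 9.4 | 6% |
| 0.5 | 50 | 38.2 | 24% |
| 1 | 100 | 60.1 | 40% |
| 2 | 200 | 81.1 | 59% |

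A simulation of 200,000 patients agrees: at L = 1 it gives 100.3 for (a), 60.2 for (b) and 100.2 for (c).

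Dependence on follow-up, with L = 1 and the same T for every patient, so that (b) = 100 × (1 − exp(−T))/T:

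- 24 weeks (T = 0.46): 80 per 100 patient-years
- 48 weeks (T = 0.92): 65
- 85 weeks (T = 1.63): 49

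Measures (a) and (c) give 100 at each length.

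Sensitivity:

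- With fixed follow-up of 0.5 to 1.84 years and L from 0.5 to 3, the shortfall of (b) runs from 12% to 82%.
- If patients differ in their underlying rate (negative binomial, dispersion 0.5 to 1.0), the shortfall at L = 1 and T = 1 is 44% to 50%, against 37% without such variation.
- For L of at most 0.1, with no such variation, it is at most 9% even at 96 weeks.

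**The case against.** The best defence is that the formula means what it says. It counts events and pairs them with total patient-years, which is a valid event rate. On that reading the shortfall is zero, a constant rate does not drift with follow-up, and the count-once sentence belongs to the tables of subjects and percentages. Event totals placed after that sentence support this. What remains is the word incidence and a rule whose scope was not limited.

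A reader might go further than the text allows and infer that the SAP does compute the rate on a count-once basis, so that recurrent events such as exacerbations will be understated by some 40% to 60%. The documents do not support this. Count-once is one of two open readings, and that range needs roughly 1 to 2 events per patient-year. The documents give no absolute exacerbation rate, only a relative difference from Study 009 in Protocol 15.2.

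The consequence is also limited. Occurrences of serious and non-serious TEAEs are tabulated, and SAP 4.9 summarises treatment duration, so a reader could approximate an all-event rate. SAP 4.11.2 reports 48-week exacerbation rates under several definitions. The SAP plans no formal comparison of TEAE rates between entry cohorts or with other studies.

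These points lower the severity but do not remove the conflict. The occurrence tables carry no person-time. The exacerbation analysis uses the respiratory event form and the ITT population, and does not cover other frequent events such as cough or upper respiratory infection (Protocol 15.3). Even the favourable reading does not deliver the incidence rate promised in Protocol 11.4.5.1.

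**Conclusion.** The point holds as a conflict between a counting rule and a formula, which leaves the numerator undefined. Under count-once, the measure is a hybrid that understates frequent recurrent events and falls with longer follow-up. Under all occurrences, it is a sound event rate with the wrong name.

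The percentages apply to the first reading only. They rest on an assumed constant hazard, the nominal 24 to 85 weeks of exposure and assumed event rates. Uncommon TEAEs would be little affected on either reading. Severity is moderate: a reader might take this as something that invalidates the safety analysis, but the raw occurrence counts and the separate exacerbation rates keep most of the information available.

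**What to change.** In SAP 4.10.1, state that the count-once rule applies to subject counts, to percentages and to the incidence rate only. Then replace the single formula with two labelled measures:

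1. *Exposure-adjusted incidence rate:* subjects with at least one event, divided by patient-time from first dose to first event, or to end of follow-up if there is none.
2. *Event rate:* all occurrences, divided by total patient-years.

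Define the end of follow-up explicitly, because the TEAE window runs to four weeks after the last dose while the present denominator counts only days on drug. Confidence intervals are optional in a descriptive study.

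The cost is a short SAP amendment, which SAP Section 1 allows before database lock, and minor programming. No new data are needed, since adverse event onset dates and dosing dates are already collected.

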In $\sim 10\%$ of patients with CF, the causative defect in the CFTR gene is a nonsense mutation that truncates CFTR protein production by introducing a premature stop codon into the CFTR messenger ribonucleic acid (mRNA). PTC Therapeutics, Inc., a biopharmaceutical company located in South Plainfield, NJ, USA has discovered and developed ataluren (PTC124®) as a novel, orally bioavailable, small-molecule drug that promotes ribosomal readthrough of mRNA containing a premature stop codon. Through this mechanism of action, ataluren has the potential to overcome the genetic defect in patients for whom a nonsense mutation causes CF. Pharmacologic proof-of-concept has been demonstrated in animal models and Phase 2 clinical trials. A Phase 3, randomized, double-blind, placebo controlled clinical trial (Study 009) of patients >6 years of age with nmCF randomized to receive ataluren 10 mg/kg in the morning, 10 mg/kg mid-day and 20-mg/kg in the evening; or placebo for 48 weeks showed positive trends favoring ataluren vs placebo for both the primary endpoint, relative change in %-predicted forced expiratory volume in 1 second (FEV₁) at Week 48, and the secondary endpoint, pulmonary exacerbation rate over 48 weeks [Kerem 2014]. A subgroup effect in FEV₁ and pulmonary exacerbation rate showing larger differences favoring ataluren was observed in patients who were not receiving chronic inhaled antibiotics, which was driven by chronic inhaled tobramycin. This same study showed that ataluren was well tolerated; safety profiles were generally similar for ataluren and placebo, other than cases of reversible Grade 3-4 creatinine elevations, which were associated with the combination of potentially nephrotoxic antibiotics with ataluren.

These encouraging data led to the conduct of a confirmatory Phase 3, international, multicenter, randomized, double-blind, placebo-controlled, efficacy and safety study (Study PTC124-GD-021-CF). This ongoing Phase 3 study includes a treatment period of 48 weeks and an estimated recruitment period of 14 months at 93 investigational sites worldwide. The first patient in study PTC124-021-CF initiated study drug treatment on 15 August 2014.

All patients who successfully complete the Phase 3 double-blind, placebo-controlled study (PTC124-GD-021-CF) will be eligible for this Phase 3 open-label, extension study (PTC124-GD-021e-CF).

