8.2.5. Post-Treatment Visits

All patients who discontinue study drug must return for a Post-Treatment Visit at the investigator site 4 weeks (\pm 7 days) after the last dose of study drug and the End of Treatment Visit, for final study-related evaluations. If the End-of-Treatment Visit occurs >4 weeks after the last dose of study drug, the Post-Treatment Visit does not need to be performed.

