9.8. Adverse Event Reporting Period

The first day of adverse event reporting will coincide with the day the first dose of study drug is administered. The adverse event reporting period for this study ends with the 4-week (\pm 7 days) Post-Treatment Follow-up Visit, except as described in Section 9.7. In addition, SAEs occurring in a patient after the study period should be reported to the sponsor if the investigator becomes aware of them.

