2. STUDY OVERVIEW

2.1. Study Design

Study 021e is a Phase 3, international, multicenter, open-label, extension study of ataluren in patients with nmCF that have completed participation in the double-blind study PTC124-GD-021-CF (Study 021).

All eligible patients that completed participation in Study 021 will be enrolled into the study. Eligible subjects will receive oral ataluren administered 3 times per day (TID) at respective morning, midday, and evening doses of 10-, 10-, and 20-mg/kg for 96 weeks. The detailed schedule of assessments are displayed in Table 1.

Screening and baseline procedures are structured to avoid a gap in treatment between the double-blind study (PTC124-GD-021-CF) and this extension study. When possible, Screening/Baseline (Visit 1) for this extension study should occur on the same day as the End-of-Study visit for the double-blind study (PTC124-GD-021-CF). During the treatment period, study assessments will be performed at clinic visits at Week 12 and thereafter every 12 weeks until the end of the study.

Planned interim safety analyses will be conducted by an independent data monitoring committee (DMC). The first safety review will occur when ~ 100 patients have completed >=36 weeks of treatment. The second safety review will occur when ~ 100 patients have completed >=72 weeks of treatment.

The study will be terminated prematurely according to company's strategic decision on March 2, 2017. All subject who are on-going by then will be discontinued.

Table 1. Schedule of Events

| Study Period | Screening/B aseline | Treatment Period | | | | | | Post-Treatment | | |
|---|---------------------|------------------|----|----|----|----|----|----------------|-----------------------------|--------------------|
| Study Week (±7 days) | Day 1 | 12 | 24 | 36 | 48 | 60 | 72 | 84 | End of Tx/ Premature D/C 96 | 4 Weeks Post-Tx |
| Visit | 1 | 2 | 3 | 4 | 5 | 6 | 7 | 8 | 9 | 10 |
| Informed consent | X | | | | | | | | | |
| CFQ-R administration | X ^a | X | X | X | X | X | X | X | X | |
| Vital signs | Xa | X | X | X | X | X | X | X | X | X |
| Height | X ^a | X | X | X | X | X | X | X | X | X |
| Weight | X ^a | X | X | X | X | X | X | X | X | X |
| Physical examination | X ^a | | | | X | | | | X | X |
| Hematology | X ^a | X | X | X | X | X | X | X | X | X |
| Biochemistry | X ^a | X | X | X | X | X | X | X | X | X |
| Urinalysis | Xa | X | X | X | X | X | X | X | X | X |
| Renal ultrasound | Xa | | | | X | | | | X | |

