4.9. Study Treatment Administration and Compliance

The study treatment duration in weeks is defined as (last dose date - first dose date +1)/7 and will be summarized overall. This duration is irrespective of the dose interruptions.

The drug compliance of a specific time period is defined as 100*(number of sachets taken during the period/number of planned sachets during the period). It will be summarized for overall treatment duration. The percentages will take into account physician-prescribed reductions and interruptions.

The number and percentage of subjects having dose interruptions and dose changes will be summarized using descriptive statistics for overall treatment duration.

The above analyses will be performed for the As-Treated population.

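### The exposure-adjusted TEAE rate counts events up to 28 days after the last dose but divides by on-drug time only, overstating the pooled rate by about 7% under stated assumptions

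*SAP*

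**What the plan says.** SAP 4.10.1 (Adverse Events) sets the TEAE window from the first dose "to 4 weeks after the last dose of study drug in this study". The same section computes a rate per 100 patient-years, by SOC and PT, as the number of events over patient-years, and fixes the denominator: "The number of patient-years is defined as the sum of the number of days on study drug of all patients divided by 365.25".

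The protocol observes the weeks after the last dose:

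- Section 8.2.5: "All patients who discontinue study drug must return for a Post-Treatment Visit at the investigator site 4 weeks" after the last dose. The visit is waived only when the End-of-Treatment Visit itself falls more than 4 weeks after that dose.
- Section 8.2.17 collects adverse events at that visit.
- Section 9.8: "The adverse event reporting period for this study ends with the 4-week" follow-up visit.

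SAP 4.9 defines treatment duration as last dose minus first dose plus one day, and adds: "This duration is irrespective of the dose interruptions". SAP 4.10.1 does not say whether its days on study drug follow that rule. Protocol 11.4.5.1 uses the same 4-week window and says only that an exposure-adjusted rate will be reported. Neither document adds follow-up time to the denominator or restricts this rate to on-drug events.

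**The concern.** A person-time rate needs events and time at risk taken over the same window. Here each patient can contribute up to 28 days of countable events with no matching time, so the rate is pushed upward wherever events occur in the tail.

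The rate belongs to the primary analyses. Because the study was ended early, patients who entered at different dates have very different exposure, and this is the adverse event summary that adjusts for it. The study has a single arm, so no within-study treatment contrast is distorted. What suffers is the level of the rate and any comparison with a rate computed on matched person-time.

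A smaller wording gap sits in the same place. The formula's numerator is best read as all occurrences. An earlier sentence in SAP 4.10.1 counts a subject with a repeated event only once and applies this to the analyses that follow, without exempting the rate.

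**Working it through.** The documents give no rate, mean exposure or total person-time, so there is no stated figure to reproduce. The size has to be built from their dates.

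**Inputs**

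- Study 021: the first patient "initiated study drug treatment on 15 August 2014"; recruitment estimated at 14 months; treatment 48 weeks, or 336 days (Protocol 1).
- SAP 2.1: "The study will be terminated prematurely according to company's strategic decision on March 2, 2017", with all ongoing subjects discontinued.
- Tail: 4 weeks = 28 days.
- About 200 patients (Protocol 5.1).

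**Assumptions:** uniform entry, no gap between the two studies, last dose on 2 March 2017 for everyone, constant event rate, tail fully followed, interruption days counted as on drug.

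**Mean exposure**

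- Extension entry: 15 Aug 2014 + 336 days = 17 Jul 2015, to 15 Oct 2015 + 336 days = 15 Sep 2016.
- Days to 2 Mar 2017: 594 for the earliest entrant (84.9 weeks), 168 for the latest (24.0 weeks).
- Mean T = (594 + 168)/2 = 381 days (54.4 weeks). Counting both end days, as SAP 4.9 does, gives 382 and the same percentage after rounding.

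**Bias.** Let λ be the on-drug event rate, r the ratio of the post-drug to the on-drug rate, and c the share of the tail followed. Expected events per patient are λ(T + 28rc). The planned rate divides this by T.

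- Planned rate over on-drug rate = 1 + 28rc/T.
- Planned rate over matched-window rate = (T + 28c)/T = 1 + 28c/T, whatever r is.
- At r = c = 1 both equal 1 + 28/381 = 1.073, so 100 events per 100 patient-years is reported as 107.3.
- At 200 patients: 200 × 381/365.25 = 208.6 patient-years on drug, and 200 × 28/365.25 = 15.3 patient-years of tail left out.

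A Poisson simulation with 200 patients, an assumed 5 events per year and 5,000 runs also gave 7.3%.

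**Sensitivity**

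| Change in assumption | Overstatement |
|---|---|
| r = 0, 0.5, 1, 2 (against the on-drug rate) | 0%, 3.7%, 7.3%, 14.7% |
| Tail 50% or 80% followed (r = 1) | 3.7%, 5.9% |
| Dropout hazard 0.1, 0.2, 0.3 per year (mean T 51.4, 48.6, 46.1 weeks) | 7.8%, 8.2%, 8.7% |
| Accrual 10, 12, 16, 18 months instead of 14 | 6.3%, 6.8%, 8.0%, 8.7% |
| Every patient at the full 96 weeks (28/672) | 4.2% |

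The dropout rows use the average of (1 − exp(−dT))/d over the entry range.

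If days on study drug excluded interruptions amounting to 5% of treatment time, the planned rate would exceed the calendar-time matched rate by (381 + 28)/(381 × 0.95) − 1 = 13.0%.

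**The case against.** The best defence is that the SAP names this a drug-exposure rate and prints its denominator, so a reader can see what was divided by what. The choice errs on the cautious side, all analyses are declared descriptive (SAP 4.2), and nothing is decided on the result. That limits the importance of the point, but it does not make the two windows agree. If on-drug time is the intended basis, the numerator should stop at the last dose.

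A second objection is that the two possible repairs estimate different things. This is correct. Extending the denominator gives a rate for the whole TEAE window; restricting the numerator gives an on-drug rate. They coincide only when the event rate is the same before and after stopping. If events ceased entirely at the last dose, the extended denominator would put the rate 28/409 = 6.8% below the on-drug rate. The sponsor must therefore choose and label the rate, but either choice is coherent and the present mixture is not.

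A third objection is that the 7% is fragile. The 14-month accrual is a protocol estimate, and 2 March 2017 may be the date of the decision and not of the last doses. Dosing that ran 28 days longer would give 28/409 = 6.8%. SAP 2.4 also raises the expected Study 021 enrolment to about 279, from about 208 in Protocol 11.1. That would change the patient-year totals if more patients rolled over, but not the percentage. The figure is an illustration and should be read as one.

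**Conclusion.** The concern holds. The numerator and denominator of a primary safety rate cover different windows, the extra 28 days are observed, and no other section reconciles them. That conclusion rests on the text alone.

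The size is conditional: 7.3% for the pooled rate under the assumptions listed, and roughly 4% to 9% across the exposure, accrual and dropout scenarios with a constant event rate and a fully followed tail. It falls towards zero if few tail events occur or are captured, and rises to 14.7% over the on-drug rate if the event rate doubles after stopping. Against a matched-window rate the factor is the same in every SOC and PT row. Against an on-drug rate it varies by row with the share of events that fall in the tail.

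This is a correction that should be made, not one that threatens the study's conclusions.

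**What to change.** Align the windows in one sentence of SAP 4.10.1, choosing one of:

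1. Patient-years run from first dose to the earlier of 28 days after the last dose and last contact, with interruption days included as in SAP 4.9. The rate is then labelled as covering the TEAE window.
2. Patient-years stay as days from first to last dose, and the rate's numerator is limited to events with onset on or before the last dose. The events in this table will then differ from those in the other TEAE tables, and a footnote should say so.

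The same sentence should state how interruption days are treated. Protocol 7.1.2 provides for interruptions during IV nephrotoxic antibiotic courses, so this bears on the renal rows. It should also state that the numerator is all occurrences and that the count-once rule does not apply to it. If subjects with at least one event are counted instead, time at risk should end at the first event.

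The cost is one sentence and a minor programming change, which SAP Section 1 allows by amendment before database lock. If the database is already locked, a footnote stating both windows, together with a matched-window rate, would serve.
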